## 8 ADVERSE EVENT REPORTING

### 8.1 Collection of Safety Information

Adverse events will be documented in the medical record and entered into PDMS/CORe according to the following guidelines...

An *Adverse Event (AE)* is defined as any new untoward medical occurrence or worsening of a pre-existing medical condition in a patient or clinical investigation subject administered an investigational (medicinal) product and that does not necessarily have a causal relationship with this treatment. An AE can therefore be any unfavorable and unintended sign (including an abnormal laboratory finding, for example), symptom, or disease temporally associated with the use of investigational product, whether or not considered related to the investigational product. Any Adverse Events considered common for this disease process (uveal melanoma, metastatic uveal melanoma) or related to disease will be captured at the discretion of the attending MD.

Adverse events can be spontaneously reported or elicited during open-ended questioning, examination, or evaluation of a subject. (In order to prevent reporting bias, subjects should not be questioned regarding the specific occurrence of one or more AEs.)

#### 8.1.1 Definition of Serious Adverse Events

A *serious AE (SAE)* is any untoward medical occurrence that at any dose:

An adverse event or suspected adverse reaction is considered “serious” if, in the view of either the investigator or the sponsor, it results in any of the following outcomes:

- Death
- A life-threatening adverse drug experience – any adverse experience that places the patient, in the view of the initial reporter, at immediate risk of death from the adverse experience as it occurred. It does not include an adverse experience that, had it occurred in a more severe form, might have caused death.
- Inpatient hospitalization or prolongation of existing hospitalization
- A persistent or significant incapacity or substantial disruption of the ability to conduct normal life functions.
- A congenital anomaly/birth defect.

Important medical events that may not result in death, be life-threatening, or require hospitalization may be considered a serious adverse drug experience when, based upon appropriate medical judgment, they may jeopardize the patient or subject and may require medical or surgical intervention to prevent one of the outcomes listed in this definition.

Examples of such medical events include allergic bronchospasm requiring intensive treatment in an emergency room or at home, blood dyscrasias or convulsions that do not result in inpatient hospitalization, or the development of drug dependency or drug abuse (21 CFR 312.32).

- **Important medical events as defined above, may also be considered serious adverse events. Any important medical event can and should be reported as an SAE if deemed appropriate by the Principal Investigator or the IND Sponsor, IND Office.**
- All events occurring during the conduct of a protocol and meeting the definition of a SAE must be reported to the IRB and BMS in accordance with the timeframes and procedures outlined in “The University of Texas M. D. Anderson Cancer Center Institutional Review Board Policy for Investigators on Reporting Unanticipated Adverse Events for Drugs and Devices”. Unless stated otherwise in the protocol, all SAEs, expected or unexpected, must be reported to the IND Office, regardless of attribution (within 5 working days of knowledge of the event).

### **8.1.2 Definition of Nonserious Adverse Event**

A *nonserious adverse event* is an AE not classified as serious.

## **8.2 Assignment of Adverse Event Intensity and Relationship to Investigational Product**

The following categories and definitions of causal relationship to investigational product as determined by a physician should be used:

- **Related:** There is a reasonable causal relationship to investigational product administration and the adverse event.
- **Not Related:** There is not a reasonable causal relationship to investigational product administration and the adverse event.

The expression “reasonable causal relationship” is meant to convey in general that there are facts (eg, evidence such as de-challenge/re-challenge) or other arguments to suggest a positive causal relationship.

## **8.3 Collection and Reporting**

- **All life-threatening or fatal events**, that are unexpected, and related to the study drug, must have a written report submitted within **24 hours** (next working day) of knowledge of the event to the Safety Project Manager in the IND Office.
- **Unless otherwise noted, the electronic SAE application (eSAE) will be utilized for safety reporting to the IND Office and MDACC IRB.**

- **Serious adverse events will be captured from the time of the first protocol-specific intervention, until 100 days after the last dose of drug, unless the participant withdraws consent. Serious adverse events must be followed until clinical recovery is complete and laboratory tests have returned to baseline, progression of the event has stabilized, or there has been acceptable resolution of the event.**
- **Additionally, any serious adverse events that occur after the 100 day time period that are related to the study treatment must be reported to the IND Office. This may include the development of a secondary malignancy.**

**Reporting to FDA:**

- **Serious adverse events will be forwarded to FDA by the IND Sponsor (Safety Project Manager IND Office) according to 21 CFR 312.32.**

**It is the responsibility of the PI and the research team to ensure serious adverse events are reported according to the Code of Federal Regulations, Good Clinical Practices, the protocol guidelines, the sponsor’s guidelines, and Institutional Review Board policy.**

**Investigator Communication with Supporting Companies:**

**All events occurring during the conduct of a protocol and meeting the definition of a SAE must be reported to the IRB and BMS in accordance with the timeframes and procedures outlined in “The University of Texas M. D. Anderson Cancer Center Institutional Review Board Policy for Investigators on Reporting Unanticipated Adverse Events for Drugs and Devices”. Unless stated otherwise in the protocol, all SAEs, expected or unexpected, must be reported to the IND Office, regardless of attribution (within 5 working days of knowledge of the event).**

**8.3.1 Serious Adverse Events**

Following the subject’s written consent to participate in the study, all SAEs must be collected, including those thought to be associated with protocol-specified procedures. All SAEs must be collected that occur within 100 days of discontinuation of dosing of the investigational product. If applicable, SAEs must be collected that relate to any later protocol-specified procedure (eg, a follow-up skin biopsy). The investigator should notify BMS of any SAE occurring after this time period that is believed to be related to the investigational product or protocol-specified procedure.

All SAEs whether related or unrelated to the ipilimumab, must be immediately reported to BMS (by the investigator or designee) within 24 hours of becoming aware of the event. If

only limited information is initially available, follow-up reports are required. The original SAE form must be kept on file at the study site.

All SAEs should be faxed or emailed to BMS at:

**Global Pharmacovigilance & Epidemiology**  
**Bristol-Myers Squibb Company**  
**[contact]**  
**Email: [[contact]](mailto:[contact])**

For studies conducted under an Investigator IND, any event that is both serious and unexpected must be reported to the FDA as soon as possible and, in no event, later than 7 days (death or life-threatening event) or 15 days (all other SAEs) after the investigator's or institution's initial receipt of the information. BMS will be provided with a simultaneous copy of all adverse events filed with the FDA. The MDACC "Internal SAE Report Form for Prompt Reporting" will be used for reporting to the IRB Office and to BMS.

All SAEs should simultaneously be faxed or e-mailed to BMS at:

**Global Pharmacovigilance & Epidemiology**  
**Bristol-Myers Squibb Company**  
**[contact]**  
**Email: [[contact]](mailto:[contact])**

Serious adverse events, whether related or unrelated to investigational product, must be recorded on the SAE page and reported expeditiously to BMS (or designee) to comply with regulatory requirements. An SAE report should be completed for any event where doubt exists regarding its status of seriousness.

All SAEs must be immediately reported by confirmed facsimile transmission (fax) and mailing of the completed SAE page. In some instances where a facsimile machine is not available, overnight express mail may be used. If only limited information is initially available, follow-up reports are required. (Note: Follow-up SAE reports should include the same investigator term(s) initially reported.) In selected circumstances, the protocol may specify conditions that require additional telephone reporting.

If the investigator believes that an SAE is not related to the investigational product, but is potentially related to the conditions of the study (such as withdrawal of previous therapy, or a complication of a study procedure), the relationship should be specified in the narrative section of the SAE page.

If an ongoing SAE changes in its intensity or relationship to the investigational product, a follow-up SAE report should be sent immediately to the sponsor. As follow-up information

becomes available it should be sent immediately using the same procedure used for transmitting the initial SAE report. All SAEs should be followed to resolution or stabilization.

The adverse events will be recorded in PDMS according to the following guidelines. The Investigator or physician designee is responsible for verifying and providing source documentation for all adverse events and assigning the attribution for each event for all subjects enrolled on the trial.

Recommended Adverse Event Recording Guidelines					
Attribution	Grade 1	Grade 2	Grade 3	Grade 4	Grade 5
Unrelated	Phase I	Phase I	Phase I Phase II	Phase I Phase II Phase III	Phase I Phase II Phase III
Unlikely	Phase I	Phase I	Phase I Phase II	Phase I Phase II Phase III	Phase I Phase II Phase III
Possible	Phase I Phase II	Phase I Phase II Phase III			
Probable	Phase I Phase II	Phase I Phase II Phase III			
Definitive	Phase I Phase II	Phase I Phase II Phase III			

### **8.3.2 Reporting to FDA**

Serious adverse events will be forwarded to FDA by the IND Sponsor (Project Manager, IND office) according to 21 CFR 312.32.

### **8.3.3 Handling of Expedited Safety Reports**

In accordance with local regulations, BMS will notify investigators of all SAEs that are suspected (related to the investigational product) and unexpected (ie, not previously described in the Investigator Brochure). In the European Union (EU), an event meeting these criteria is termed a Suspected, Unexpected Serious Adverse Reaction (SUSAR). Investigator notification of these events will be in the form of an expedited safety report (ESR).

In addition, suspected serious adverse reactions (whether expected or unexpected) shall be reported by local IRB to the relevant competent health authorities in all concerned countries according to local regulations (either as expedited and/or in aggregate reports).

### **8.3.4 Nonserious Adverse Events**

The collection of nonserious AE information should begin at initiation of investigational product. If an ongoing nonserious AE worsens in its intensity, or if its relationship to the investigational product changes, a new nonserious AE entry for the event should be completed. Nonserious AEs should be followed to resolution or stabilization, or reported as SAEs if they become serious. Follow-up is also required for nonserious AEs that cause interruption or discontinuation of investigational product, or those that are present at the end of study participation. Subjects with nonserious AEs at study completion should receive post-treatment follow-up as appropriate.

All identified nonserious AEs must be recorded and described in the medical record.

### **8.3.5 Pregnancy**

Sexually active WOCBP must use an effective method of birth control during the course of the study, in a manner such that risk of failure is minimized. Before enrolling WOCBP in this clinical study, the investigator must review the guideline about study participation for WOCBP which can be found in the GCP Manual for Investigators. The topics include the following:

- General Information
- Informed Consent Form
- Pregnancy Prevention Information Sheet
- Drug Interactions with Hormonal Contraceptives
- Contraceptives in Current Use

- Guidelines for the Follow-up of a Reported Pregnancy.

Before study enrollment, WOCBP must be advised of the importance of avoiding pregnancy during study participation and the potential risk factors for an unintentional pregnancy. The subject must sign an informed consent form documenting this discussion.

**All WOCBP MUST have a negative pregnancy test within 72 hours before receiving ipilimumab.** The minimum sensitivity of the pregnancy test must be 25 IU/L or equivalent units of HCG. If the pregnancy test is positive, the subject must not receive ipilimumab and must not be enrolled in the study.

Women of childbearing potential (WOCBP) and fertile men with partners of childbearing potential must be using an adequate method of contraception to avoid pregnancy throughout the study and for up to 26 weeks after the last dose of investigational product.

**In addition, all WOCBP should be instructed to contact the investigator immediately if they suspect they might be pregnant (e.g., missed or late menstrual period) at any time during study participation.**

If, following initiation of the investigational product, it is subsequently discovered that a study subject is pregnant or may have been pregnant at the time of investigational product exposure, including during at least 6 half-lives after product administration, the investigational product will be permanently discontinued in an appropriate manner (eg, dose tapering if necessary for subject safety). The investigator must immediately notify BMS of this event and record the pregnancy on the Pregnancy Surveillance Form (not an SAE form). Initial information on a pregnancy must be reported immediately to BMS, and the outcome information provided once the outcome is known. Completed Pregnancy Surveillance Forms must be forwarded to BMS according to SAE reporting procedures.

Any pregnancy that occurs in a female partner of a male study participant should be reported to the sponsor. Information on this pregnancy will be collected on the Pregnancy Surveillance Form.

Protocol-required procedures for study discontinuation and follow-up must be performed on the subject unless contraindicated by pregnancy (e.g., x-ray studies). Other appropriate pregnancy follow-up procedures should be considered if indicated. In addition, the investigator must report to BMS, and follow-up on information regarding the course of the pregnancy, including perinatal and neonatal outcome. Infants should be followed for a minimum of 8 weeks.

### **8.3.6 Other Safety Considerations**

Any significant worsening noted during interim or final physical examinations, electrocardiograms, x-rays, and any other potential safety assessments, whether or not these procedures are required by the protocol, should also be recorded in the medical record.

## **9. Statistical Methodology**

The trial originally used Simon's two-stage design to target a response rate of 15% vs. a historical rate of 5%. A total of 30 patients were to have been enrolled in the first stage, and if at least two had responded, an additional 22 patients would have been enrolled in the second stage. Given advancements in melanoma treatment, a 15% response rate is no longer considered interesting, and in 2017, the study has been changed to a single-stage design targeting a response rate of 20%. A total of 23 evaluable patients have been enrolled at the time of this change.

A single-stage trial design will be employed to enroll patients on the metastatic arm with the following assumptions:

- Type I error rate of 5%, power of 80%
- Null hypothesis of 5% response rate
- Alternate hypothesis of 20% response rate
- Response will be defined as those patients who achieve RECIST CR + PR.
- Accounting for attrition (inevaluable patients, 25%) and screen fails (5%), up to 39 patients are needed to achieve a target enrollment of 27 evaluable patients.
- If at least 4 of the 27 patients are responders, the null hypothesis of a 5% response rate will be rejected in favor of the alternative hypothesis.

If the true probability of response is 5%, this design has a 4.4% chance of incorrectly concluding that it is effective. If the true probability of response is 20%, the design has an 18.2 % chance of incorrectly concluding that it is not effective.

Safety Analysis at baseline, a medical history will be obtained to capture relevant underlying conditions. The baseline examinations should include weight, height, ECOG Performance Status, BP, HR, temperature and oxygen saturation by pulse oximetry at rest and after exertion and should be performed as noted in Table 10 Notes Baseline signs and symptoms are those that are assessed within 14 days prior to randomization. Concomitant medications will be collected from within 14 days prior to randomization through the study treatment period.

Baseline local laboratory assessments should be done within 14 days prior to treatment to include: CBC w/differential, LFTs (ALT, AST, total bilirubin, alkaline phosphatase), BUN or serum urea level, creatinine, Ca, Mg, Na, K, Cl, LDH, glucose, amylase, lipase, TSH, Free T4, Free T3, and Hep B and C testing only as clinically indicated (HBV sAg, HCV Ab or HCV RNA). Pregnancy testing for WOCBP (done locally) must be performed within 24 hours prior to the initial administration of study drug at baseline and then within 24 hours of dosing at Week 1 and Week 4 of cycle 1 and , 3 and Week 1 and Week 5 starting from cycle 5 and at the safety follow up visits.

Subjects will be evaluated for safety if they have received any study drug. Toxicity assessments will be continuous during the treatment phase. During the safety follow-up phase, toxicity assessments should be done in person. Once subjects reach the survival follow-up phase either in person or documented telephone calls to assess the subject's status are acceptable.

Adverse events and laboratory values will be graded according to the NCI-CTCAE version 4.0.

On-study weight and ECOG Performance status should be assessed on Day 1 of Weeks 1, 3, 4 and 5 during cycles 1 and 2 (except Cycle 1 Day 1) and Day 1 of Weeks 1, 3 and 5 starting from Cycle 3 and vital signs should be assessed at each on-study visit (except Cycle 1 Day 1). Vital signs should also be taken as per institutional standard of care prior to, during and after dosing. Oxygen saturation by pulse oximetry at rest and after exertion should be assessed at each on-study visit prior to dosing. The start and stop time of the

nivolumab infusion should be documented. Physical examinations are to be performed as clinically indicated. If there are any new or worsening clinically significant changes since the last exam, report changes on the appropriate non-serious or serious adverse event page.

On study local laboratory assessments should be done within 72 hours of dosing to include; CBC w/differential, LFTs (ALT, AST, total bilirubin, alkaline phosphatase), BUN or serum urea level, creatinine, Ca, Mg, Na, K, Cl, LDH, glucose, amylase, lipase, TSH with Free T4, Free T3 on Day 1 of Weeks 1, 4, 7, 10 and 13, then every 12 weeks. Additional measures including non-study required laboratory tests should be performed as clinically indicated or to comply with local regulations. Laboratory toxicities (eg, suspected drug induced liver enzyme elevations) will be monitored during the follow-up phase via on site/local labs until all study drug related toxicities resolve, return to baseline or are deemed irreversible.

Oxygen saturation by pulse oximetry should be obtained prior to each dosing and at any time a subject has any new or worsening respiratory symptoms. A reading at rest and on exertion should be obtained at each time point. The extent of the exertion should be based on the judgment of the investigator, but should remain consistent for each individual subject throughout the study. If the patient's status changes, the investigator can alter the extent of exertion based on their medical judgment. If a subject shows changes on pulse oximetry or other pulmonary related signs (hypoxia, fever) or symptoms (eg, dyspnea, cough, fever) consistent with possible pulmonary adverse events, the patient subject should be immediately evaluated to rule out pulmonary toxicity. An algorithm for the management of suspected pulmonary toxicity can be found in the nivolumab Investigator's Brochure.

Some of the previously referred to assessments may not be captured as data in the eCRF. They are intended to be used as safety monitoring by the treating physician. Additional testing or assessments may be performed as clinically necessary or where required by institutional or local regulations.

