### **1.3.7.a Rationale for Using Immune-Related Tumor Assessment Criteria (irRC)**

Ipilimumab is an immuno-stimulating antibody with evidence of anti-cancer activity (durable objective response and stable disease) in subjects with advanced melanoma, including subjects with established brain disease. Observations of clinical activity defined by tumor response endpoints defined by conventional criteria (eg, mWHO) may be inadequate to realize the kinetics and magnitude of clinical benefit achieved with ipilimumab.

Histopathologic evidence has demonstrated ipilimumab can produce an influx or expansion of tumor infiltrating lymphocytes. Therefore, early increases in lesion size detected radiologically or upon gross examination could be misinterpreted as progressive tumor growth and precede objective tumor shrinkage. In addition the appearance of new lesions may have categorized a subject to have progressive disease using conventional tumor assessment criteria despite the concurrent observation of objective tumor responses in pre-existing lesions and a net reduction in global tumor burden that includes the new lesions.

Hence the appearance of new lesions in and of themselves may not necessarily constitute progressive disease. The immune-related response criteria (irRC) were developed as a tool to gauge tumor response using the changes in global tumor burden. In addition, the irRC may be useful to inform a physician's decision to continue dosing in subjects who may receive benefit from additional ipilimumab therapy. The ir-response assessment is based solely on objective measurements (SPD) of index and new lesions. Non-index lesions are not considered.

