### 6.4.2 Efficacy Evaluation

All efficacy evaluations will be conducted by the investigator or their designee using the response criteria established by the World Health Organization (WHO). All subject's results will be documented in the subject's eCRF.

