#### **6.4.3.c Impact of New Lesions on irRC**

New lesions in and by themselves do not qualify as progressive disease. However their contribution to total tumor burden is included in the SPD which in turn feeds into the irRC criteria for tumor response. Therefore, new non-measurable lesions will not discontinue any subject from the study.

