#### **6.4.3.d Definition of Overall Response Using irRC**

Overall response using irRC will be based on these criteria:

- **Immune-Related Complete Response (irCR):** Complete disappearance of *all* tumor lesions (index and nonindex together with no new measurable/unmeasurable lesions) for at least 4 weeks from the date of documentation of complete response.
- **Immune-Related Partial Response (irPR):** The sum of the products of the two largest perpendicular diameters of all index lesions is measured and captured as the SPD baseline. At each subsequent tumor assessment, the sum of the products of the two largest perpendicular diameters of all index lesions and of new measurable lesions are added together to provide the Immune Response Sum of Product Diameters (irSPD). A decrease, relative to baseline of the irSPD compared to the previous SPD baseline, of 50% or greater is considered an immune Partial Response (irPR).
- **Immune-Related Stable Disease (irSD):** irSD is defined as the failure to meet criteria for immune complete response or immune partial response, in the absence of progressive disease.
- **Immune-Related Progressive Disease (irPD):** It is recommended in difficult cases to confirm PD by serial imaging. Any of the following will constitute progressive disease:
  - At least 25% increase in the sum of the products of all index lesions over baseline SPD calculated for the index lesions.
  - At least a 25% increase in the sum of the products of all index lesions and new measurable lesions (irSPD) over the baseline SPD calculated for the index lesions.

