**6.4.3.e Immune-Related Best Overall Response Using irRC (irBOR)**

irBOR is the best confirmed irRC overall response over the study as a whole, recorded between the date of first dose until the last tumor assessment before subsequent therapy (except for local palliative radiotherapy for painful bone lesions) for the individual subject in the study. For the assessment of irBOR, all available assessments per subject are considered.

irCR or irPR determinations included in the irBOR assessment must be confirmed by a second (confirmatory) evaluation meeting the criteria for response and performed no less than 4 weeks after the criteria for response are first met.

For metastatic patients, imaging of the chest, abdomen and pelvis is required at screening (ie, baseline) and at each tumor assessment visit, regardless of the location of known metastases. Refer to Section 6.1 Time and Events Schedule for further information. Similar methods of tumor assessment and similar techniques must be used to characterize each identified and reported lesion at screening and during subsequent tumor assessments. Imaging-based evaluation is preferred to clinical examination. For adjuvant patients, imaging of the chest, abdomen and pelvis is required at baseline and at Week 24 (+/- 7 days) and every 6 months thereafter (+/- 7 days) until removal from or completion of study.

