#### **6.4.4 Response Endpoints**

Nivolumab and ipilimumab are expected to trigger immune-mediated responses, which require activation of the immune system prior to the observation of clinical responses. Such immune activation may take weeks to months to be evident. Some patients may have objective volume increase of tumor lesions or other disease parameters (based on study indication, ie, hematologic malignancies) within 12 weeks following the start of ipilimumab dosing. Such patients may not have had sufficient time to develop the required immune activation or, in some patients, tumor volume or other disease parameter increases may represent infiltration of lymphocytes into the original tumor or blood. In conventional studies, such tumor volume or relevant laboratory parameter increases during the first 12 weeks of the study would constitute PD and lead to discontinuation of imaging to detect response, thus disregarding the potential for subsequent immune-mediated clinical response.

Therefore, patients with tumor volume increase detected or lack of laboratory parameter response documentation prior to week 12 but without rapid clinical deterioration should continue to be treated and clinically observed with a stringent imaging schedule to allow detection of a subsequent tumor response. This will improve the overall assessment of the clinical activity of ipilimumab and more likely capture its true potential to induce clinical responses. Tumor assessments will be made using modified WHO criteria.

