## **9.1 Efficacy Analysis**

Study evaluations will take place in accordance with the flow charts in Section 5.1. Baseline assessments should be performed within 28 days prior to randomization utilizing CT or MRI. In addition to chest, abdomen, pelvis, and brain, all known sites of disease should be assessed at baseline. Subsequent assessments should include chest, abdomen, and pelvis, and all known sites of disease and should use the same imaging method as was used at baseline. Subjects will be evaluated for tumor response beginning 12 weeks (+/ 1 week) from randomization and continuing every 6 weeks ( $\pm$  1 week) for the first 12 months from randomization and every 12 weeks (+/ 1 week) thereafter, until disease progression is documented or treatment is discontinued (whichever occurs later). Tumor assessments for ongoing study treatment decisions will be completed by the investigator using RECIST (Response Evaluation Criteria in Solid Tumors) 1.1 criteria.

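### The 4-of-27 rule counts RECIST responses, but Section 6.4 has efficacy read by WHO, modified WHO and irRC, and nothing says which governs

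*Combined protocol and SAP*

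**What the plan says.** The primary objective (Section 2.1) is overall response rate, with no criteria named. The criteria appear in several other places:

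- **Synopsis (Statistics) and Section 9**, in the same list as the hypotheses: "Response will be defined as those patients who achieve RECIST CR + PR". Section 9 adds the rule that at least 4 responders among 27 rejects the 5% null. It gives neither a RECIST version nor a confirmation rule.
- **Section 6.4.2**: "All efficacy evaluations will be conducted by the investigator or their designee using the response criteria established by the World Health Organization (WHO").
- **Section 6.4.4**, headed Response Endpoints: "Tumor assessments will be made using modified WHO criteria".
- **Sections 6.4.2.b to 6.4.3.e** write out irRC: a sum of products of two diameters over up to ten index lesions, with new measurable lesions added later. A fall "of 50% or greater is considered an immune Partial Response (irPR"). For best overall response, irCR and irPR "must be confirmed by a second (confirmatory) evaluation meeting the criteria for response and performed no less than 4 weeks after" the first.
- **Section 9.1**: "Tumor assessments for ongoing study treatment decisions will be completed by the investigator using RECIST", version 1.1. It does not say whether this also covers the response count.
- **Section 1.3.7.g** refers to progression by RECIST 1.1 when it allows continued treatment.

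**The concern.** The sections that tell the investigator how to read scans and the section that tells the statistician what to count name different criteria. Section 6.4 contains no RECIST lesion or response definitions, so measurements taken as it directs would be bidimensional WHO or irRC readings.

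The protocol itself says the criteria can classify the same scans differently. Section 1.3.7.a explains that "the appearance of new lesions may have categorized a subject to have progressive disease using conventional tumor assessment criteria", even when existing lesions are responding and total burden has fallen. Section 6.4.3.c says "New lesions in and by themselves do not qualify as progressive disease".

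The trial is single-arm and open-label, and the investigator reads the response. If the conflict is still open when results are known, the criterion could be chosen, even without intent, by the count it gives. The stated error rates would not cover that choice.

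**Working it through.** **1. Reproduce the plan's figures.** Inputs from Section 9: n = 27, cut-off 4, null rate 5%, alternative 20%. With X binomial(27, p):

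- Type I error = P(X ≥ 4 | p = 0.05) = 0.0437. The plan says 4.4%.
- Power = P(X ≥ 4 | p = 0.20) = 0.8177, so type II error = 1 − 0.8177 = 0.1823. The plan says 18.2%.

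Both match. 27 is also the smallest n that reaches 80% power with type I error at or below 5%; n = 26 gives 79.3%.

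**2. How far one patient moves the rule.** This is an illustration, not an estimate. If the criterion used always adds one responder to the count that Section 9 intends, the effective cut-off on that count is 3. If it always removes one, the effective cut-off is 5.

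| Effective cut-off (n = 27) | Type I error at 5% | Power at 20% |
|---|---|---|
| 3 | 15.0% | 92.8% |
| 4 (plan) | 4.4% | 81.8% |
| 5 | 1.0% | 65.2% |

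**3. When one patient reverses the conclusion.** A one-patient shift matters only at the boundary.

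| Event | True rate 5% | True rate 20% |
|---|---|---|
| X = 3 (one added responder turns failure into success) | 10.7% | 11.1% |
| X = 4 (one removed responder turns success into failure) | 3.4% | 16.6% |

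The tables agree: 0.0437 + 0.1068 = 0.1505, and 0.8177 − 0.1658 = 0.6519.

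**4. The only comparison of criteria in the documents.** Section 1.3.7 reports the earlier melanoma combination study: 21 of 52 responders by modified WHO (40.4%). It lists three further immune-related partial responses, one each in Cohorts 1, 2a and 3. Adding them gives 24 of 52 (46.2%). If a 5% null rate rose in the same proportion, it would be 0.05 × 24/21 = 5.7%, and P(X ≥ 4 | 27, 0.057) = 6.5%. This compares modified WHO with immune-related criteria, not with RECIST, and Section 1.6 says that study enrolled no uveal melanoma patients. It shows that counts depend on the criterion; it does not give the size here.

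**5. Null rates that differ by criterion (assumed values).** If 5% under one system were 6%, 7% or 8% under another, the chance of at least 4 of 27 would be 7.6%, 11.7% or 16.6%.

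**The case against.** The strongest reply is that the test already has one criterion. Section 9 puts RECIST in the same list as the 4-of-27 rule, the synopsis repeats it, and nothing ties that rule to WHO, modified WHO or irRC. A specific definition in the statistical section would normally govern. That reading is reasonable, and the fix below adopts it. It is not conclusive, because Section 6.4.2 covers all efficacy evaluations and Section 9.1 gives RECIST 1.1 a treatment-decision role only. It also leaves version and confirmation unstated.

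A second reply is that the 15.0% and 65.2% figures overstate the matter. Always adding one responder lifts the expected null count from 1.35 (27 × 0.05) to 2.35, whereas the earlier study suggests about a 14% increase (24/21) and a type I error near 6.5%. This stands as a limit on magnitude: the larger figures describe a one-patient shift and should not be read as expected inflation.

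Third, the new-lesion passages concern progression rather than response, and RECIST thresholds appear nowhere in the documents, so the divergence between RECIST and Section 6.4 cannot be measured from them. This is correct as to size. Section 1.3.7.a does, however, describe a patient with shrinking lesions and falling total burden who is labelled as progressing.

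Finally, WHO and modified WHO may be loose names for one system, and irRC partly serves decisions on continued dosing. Even so, Section 6.4.3.e defines a confirmed best overall response by irRC, so at least two systems compete for the response count.

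**Conclusion.** The concern holds. The primary responder definition is contradictory across sections, and following Section 6.4 as written would not yield the endpoint tested in Section 9. This should be corrected before the final response count.

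The sample size, the cut-off and the stated 4.4% and 18.2% are correct and are not in question. They are valid for a single criterion fixed in advance. The consequence is concentrated at counts of 3 and 4. The effect sizes above assume either a fixed one-patient shift or a hypothetical change in the null rate; the documents establish neither the size nor the direction of the difference between criteria in this trial.

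**What to change.** State once that RECIST 1.1 CR + PR governs the primary response count, taking the criterion from Section 9 and the version from Sections 9.1 and 1.3.7.g. Then:

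- Amend Sections 6.4.2 and 6.4.4 to match, and say in Section 9.1 that RECIST 1.1 applies to the efficacy analysis.
- Label WHO, modified WHO and irRC results, including irBOR, as supportive.
- State before the final count whether confirmation is required. Reporting both confirmed and unconfirmed counts would be a useful addition, secondary to naming the criterion.
- Fix RECIST target lesions from baseline scans without reference to response. Section 9 notes that 23 evaluable patients had already been enrolled when the single-stage design was adopted, so some of this may be retrospective.

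The cost is amendment wording, target-lesion selection and recalculation of sums from recorded measurements. The sample size, cut-off and error rates do not change. There are two downsides. Responses seen only by irRC or WHO would not count toward the 4. Confirmed counts may also be incomplete, because Section 3.4 leaves efficacy assessments to standard of care after removal for toxicity or investigator judgment.
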